### **2.2.2. Sample Size and Power**

The number of patients is determined by using Simon's 2-stage design (Simon 1989).

A large black rectangular box covers the majority of the page below the text, indicating that the sample size and power information has been redacted.

Patients are considered efficacy-evaluable if they received at least 1 dose of study drug and have measurable disease by investigator assessment at baseline. Efficacy-evaluable patients who don't have post-baseline disease assessment will be considered as non-responders.

Sample size determination for each cohort is specified in Table 1.

**Table 1: Sample Size Determination**

	Null/Alternative Hypotheses	Study Power	Study alpha (1-sided)	Stage 1 n (minimum number of responses to move to Stage 2)	Total Study N (minimum number of responses for trial success)
Melanoma cohort	[REDACTED]	[REDACTED]	[REDACTED]	[REDACTED]	[REDACTED]
Tissue agnostic cohort	[REDACTED]	[REDACTED]	[REDACTED]	[REDACTED]	[REDACTED]

Enrollment per cohort may be terminated early independently of each other. No adjustment for multiple hypothesis testing will be made if both cohorts complete enrollment.

## 2.3. Planned Analyses

### 2.3.1. Interim Analysis

An informal interim analysis of melanoma and tissue agnostic cohort may occur when all stage 1 patients in each cohort have been followed for a minimum of approximately 6 months, respectively.

Once outstanding data queries have been resolved, the database will be locked, and the informal interim analysis of the study will be performed.

As indicated in Section 2.2.1, this interim analysis will not occur due to early study termination.

### 2.3.2. Primary Analysis

The primary analysis for melanoma and tissue agnostic cohorts will occur when all stage 1 and 2 patients (as applicable) enrolled in each cohort have been followed for a minimum of approximately 6 months, respectively. Once outstanding data queries have been resolved, the database will be locked, and the primary analysis of the study will be performed.

As indicated in Section 2.2.1, this primary analysis will not occur due to early study termination.

### 2.3.3. Final Analysis

Because of the early study termination, all patients will end study after being followed for at least 6 months after the first dose of study drug. At the end of the study, when the last visit occurs for the last patient enrolled, outstanding data queries have been resolved or adjudicated as unresolvable, and the data have been cleaned and finalized, the final analysis of the data will be performed. Once outstanding data queries have been resolved, the database will be locked, and the final analysis of the study will be performed.

### 2.3.4. Independent Data Monitoring

An Independent Data Monitoring Committee (IDMC) has been assembled under a dedicated charter specifically developed for safety oversight of DAY101-102 studies. The detailed roles and responsibilities of the IDMC and the scope of analysis to be provided to the IDMC are

provided in a mutually agreed upon charter, which defines the IDMC membership, meeting logistics, and meeting frequency.

IDMC safety data review meetings will occur approximately every 3 months as per protocol. After the first year of review, the IDMC may recommend a more appropriate meeting frequency based on the enrollment. The specific frequency of these reviews will depend upon the rate at which the trial is enrolled, the nature of any emerging safety signals, and monitoring recommendations from the IDMC. At each review, all available safety data will be summarized and evaluated. The IDMC provides advice to the Sponsor as outlined in the IDMC charter.

### **2.3.5. Randomization and Blinding Procedures**

There is no randomization in this study. Patients will be enrolled into either a melanoma cohort or a “tissue-agnostic” cohort.

### **2.3.6. Efficacy Assessments**

Tumors will be assessed by radiographic tumor measurements using CT and/or MRI. Tumor response disease assessments will be conducted in accordance with Table 2: Schedule of Events. The primary method for tumor response disease assessments will be by RECIST version 1.1. The alternative criteria of assessment that may be used will be RANO ([Wen et al. 2017](#)). Regardless of study treatment discontinuations, tumor assessment will progress accordingly as if on study treatment and these patients will be requested to return to site for continued monitoring and assessment.

The overall tumor burden will be estimated at baseline and subsequent measurements. Measurability of a tumor lesion will be evaluated by contrast-enhancing CT and/or MRI, and the presence of at least one measurable lesion will be characterized as measurable disease.

Additionally, date of death or last follow-up will be recorded for each patient.

### **2.3.7. Safety Assessments**

Safety assessments include clinical laboratory tests, vital signs, physical examinations, ophthalmologic exam, visual acuity, clinical adverse events, 12-lead resting ECG (performed in triplicate), and ECHO/MUGA. These assessments will be conducted according to Table 2: Schedule of Events.

Clinical laboratory tests include:

- Hematology: hemoglobin, hematocrit, red blood cell count, white blood cell count with differential (neutrophils [count and percentage], lymphocytes, monocytes, eosinophils, basophils), and platelet count
- Chemistry: alkaline phosphatase, albumin, ALT, AST, CPK, BUN, creatinine, creatinine clearance, glucose, lactate dehydrogenase, total and direct bilirubin, total protein, sodium, serum calcium, phosphate, magnesium, and potassium.
- Coagulation: Prothrombin Time (PT)/International Normalized Ratio (INR), and activated prothrombin time (PTT).

- Thyroid Function Tests: thyroid stimulating hormone (TSH), and free tetraiodothyronine (free T4), and reflexive triiodothyronine (T3) may be obtained.
- Urine or Serum pregnancy test.

Vital sign measurements include:

- Body temperature
- Heart rate
- Respiratory rate
- Systolic and diastolic blood pressure
- Oxygen saturation

Physical examinations include a review of systems such as extremities, genitourinary, head/ears/eyes/nose/throat, lymph nodes, musculoskeletal, pulmonary, and skin. Any symptoms related to skin discomfort, visual disturbance and cardiopulmonary will also be assessed.

The investigator will evaluate any laboratory abnormalities or other safety assessments for clinical significance, and clinically significant abnormalities will be recorded as adverse events (AEs). Abnormal laboratory findings that result in new or worsening clinical sequelae, require therapy, or adjustment in current therapy will be considered AEs and analyzed according to NCI Common Terminology Criteria for Adverse Events (CTCAE) v5.0.

### **2.3.8. Other Assessments**

- Demographics,
- Medical history,
- Eastern Cooperative Oncology Group Status/Lansky Performance Status,
- Height and weight, Bone age (patients aged 18 years or less),
- Assessment of Change in Pubertal Development (Tanner Stage) (patients < 18 years of age),
- Visual symptom assessment,
- Dermatologic Examination,
- Neurologic Examination,

In addition, archival and fresh tumor samples, ctDNA, plasma concentrations of tovorafenib for pharmacokinetic assessments, assay tumor biopsies for pharmacodynamic assessments, and concomitant medication use will be collected in accordance with Table 2: Schedule of Events.

**Table 2: Schedule of Events**

Assessment	
Informed consent/ assent b	
Demographics	
Medical History	
ECOG or Lansky (for patients <16 years of age)	
Physical examination c	
Neurologic Examination d	
Dermatologic Examination d	
Bone Age e	
Tanner Staging f	
Vital signs g	
12-lead ECG in triplicate g	
Hematology h	
Chemistry h	
Creatine phosphokinase h	
Coagulation Panel (APTT/INR) i	
Thyroid function test i	
HBcAb, HBsAg, HCV RNA j	
HIV-1 Ab, HIV-2 Ab, HIV viral load and CD4+ T cell count j	
Echocardiogram/MUGA k	
Ophthalmologic exam l	
Visual symptom assessment m	
Pregnancy test n	
Adverse events o	

Assessment	
Concomitant medication p	
Tumor assessment CT/MRI q	
Archival tumor tissue samples r	
Freshly acquired tumor tissue sample (PD analysis) s,t	
PK Sample u, v	
ctDNA v	
Additional anticancer treatment and survival status w	
Tovorafenib dosing x	
Tovorafenib Drug Dosing Diary y	
Tovorafenib drug Dispensation/Return z	

a Results of screening assessments must be reviewed by Investigator before patient enrollment to confirm that the patient meets the eligibility criteria.

b Informed consent may be obtained greater than [REDACTED] but must be provided before any study-specific procedures are performed; however, evaluations performed as part of routine care prior to informed consent can be utilized as screening evaluations if permitted by site IRB/IEC policies.

Assessments will be performed at the end of [REDACTED]

[REDACTED]. Assessments are to be performed on or up to 7 days before the next cycle. For CT/MRI, assessments are to be performed per the protocol-defined schedule regardless of whether study treatment is discontinued. To ensure image consistency, the same imagine modalities and acquisition protocols used at Screening are to be used for subsequent tumor assessments.

c A complete physical examination, including weight, height, and vital signs will be performed [REDACTED] for all subjects. At subsequent physical exams only patients ages 12 to <18 should have height and weight collected. The physical exams will take place prior to the start of dosing of each [REDACTED]; otherwise, a symptom-directed physical examination will be done.

d All patients: A baseline complete neurologic examination should be performed by the Investigator and/or a neurologist. Symptom directed neurologic examinations will be completed at subsequent visits as indicated. A baseline complete dermatologic examination should be performed by the Investigator and/or a dermatologist. Symptom directed dermatologic examinations will be completed at subsequent visits as indicated. Tissue Agnostic Cohort: Patients with CNS tumors will have complete neurologic examinations performed at baseline and at subsequent visits as indicated.

e All patients aged 18 years or less should have an assessment of bone age at baseline via bone age radiograph of the left wrist. For patients aged 12-18 years of age without epiphyseal closure at baseline, bone age via radiograph should be assessed [REDACTED] thereafter.

f For patients 12 to < 18 years of age, pubertal stage will be measured [REDACTED] thereafter. For female patients, age at menarche will be recorded. Assessments will occur while on active treatment through sexual maturity. Refer to Study Protocol DAY101-102 (Master Protocol Section 6.9) for Tanner Staging details.

g Vitals performed on days where pharmacokinetic (PK) collection occurs should be performed prior to collection. ECGs should be collected immediately before PK sample collections on days/timepoints when PK sampling occurs (within 15 minutes prior to the PK collection). Patients will rest at least 5 minutes prior to obtaining ECGs.

h Assessment will be performed at [REDACTED]

i Assessment will be performed at [REDACTED] and as clinically indicated.

### **3. STATISTICAL METHODS**

#### **3.1. General Methods**

##### **3.1.1. Computing Environment**

All statistical analyses will be performed using SAS® Version 9.4 or higher in a secure and validated environment.

##### **3.1.2. Reporting of Numerical Values**

Relevant descriptive statistics (n, mean, standard deviation, median, minimum, and maximum) will be calculated for continuous variables. Confidence intervals (CIs) will be provided where appropriate.

Frequencies and percentages will be presented for categorical and ordinal variables, with the frequencies reported as integers and percentages reported with one decimal place. Unless otherwise specified, the percentages will be calculated based on the total number of patients included for the analysis group. Frequencies and percentages for patients with missing data may be presented.

Means, medians, and confidence intervals will be reported to one decimal place more than the data reported on the case report form (CRF) or by the laboratory/vendor. Standard deviations will be reported to two decimal places more than the data.

A month is operationally defined to be 30.4375 days. Six months is operationally defined to be 182.625 days. One year is defined to be 365.25 days.

##### **3.1.3. Baseline Value and Change from Baseline**

Baseline value will be defined as the most recent non-missing value obtained prior to administration of first dose of study treatment. Change from baseline will be calculated by subtracting the baseline value from the relevant post-baseline assessment for each patient (i.e., post-baseline – baseline).

##### **3.1.4. Handling of Missing/Incomplete Values**

Unless otherwise explicitly specified, missing data will not be imputed; observed values will be used in the analyses.

##### **3.1.5. Handling of Repeated Assessments**

If multiple results are available for a post-dose assessment at the same scheduled time point, then the worst observation (eg, highest CTCAE grade or further away from the normal range for laboratory results, the highest value for vital signs) will be used in all descriptive summaries. All results will be displayed in patient data listings, and abnormal values will be flagged, where applicable.

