7.3.2.3. Vital Signs

All patients will have pretreatment baseline vital signs and pre-dose measurements as described in the Schedule of Activities in the relevant sub-protocol. The results for each vital sign will be summarized in a descriptive manner by calculating the mean, standard deviation, median, and range by time point in the same manner described for laboratory values. For these analyses, the minimum, maximum, average, and last post-baseline value will be determined relative to the baseline vital sign measurements only.

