### **3.1.7.2. Analysis Visit Windows**

No analysis visit windows will be identified for the safety summaries. Visit-based data summaries will be based on the protocol scheduled visits.

If more than one assessment is available for a given post-baseline visit, the worst observation will be selected for visit-based summaries.

Any data relating to unscheduled visits will not be assigned to a particular visit or time point. However, the following exceptions will be made:

- Unscheduled visit prior to first dose of study drug may be included in the calculation of baseline value if applicable.
- Unscheduled visits after the first dose of study drug will be considered in summaries for the extreme post-baseline value.

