#### **3.3.3.3. Vital Signs**

Vital signs include systolic and diastolic blood pressure, heart rate, respiratory rate, oxygen saturation, and body temperature.

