### **3.3.3.7. Electrocardiograms (ECGs)**

ECG parameters include heart rate (bpm), PR (msec), RR (msec), QRS (msec), QT (msec), and QTcF (msec). ECGs will be collected in triplicate at select timepoints (Screening, [REDACTED] and [REDACTED]) after ensuring patient has been resting for at least 5 minutes. For all continuous ECG measurements, triplicate data at each timepoint will be averaged prior to analysis.

Each ECG reading will also be categorized as normal or abnormal based on the interpretation of the assessment by the investigator and, if deemed abnormal, will also be categorized as clinically significant or not clinically significant.

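### The SAP's example of the worst repeated vital sign, the highest value, points the wrong way for oxygen saturation

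*SAP*

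**What the plan says.** SAP 3.1.5 covers several results at one scheduled post-dose time point. The value carried into all descriptive summaries is "the worst observation (eg, highest CTCAE grade or further away from the normal range for laboratory results, the highest value for vital signs". Every result still goes into the listings, with abnormal values flagged where applicable.

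Oxygen saturation falls under the vital-signs part of that rule. SAP 3.3.3.3 states: "Vital signs include systolic and diastolic blood pressure, heart rate, respiratory rate, oxygen saturation, and body temperature". The list in SAP 2.3.7 includes "Oxygen saturation", and Protocol 6.10 also counts it as a vital sign.

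Other provisions that bear on the point:

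- SAP 3.1.7.2 repeats the principle for visits with more than one assessment, without a direction: "the worst observation will be selected for visit-based summaries". It leaves unscheduled results unassigned to any visit, but adds: "Unscheduled visits after the first dose of study drug will be considered in summaries for the extreme post-baseline value".
- SAP 3.3.3.7 gives ECG replicates their own rule: "triplicate data at each timepoint will be averaged prior to analysis". SAP 3.3.3.3 has no such rule for vital signs.
- SAP 3.8 names vital signs in its opening paragraph but has no vital-signs subsection.
- Protocol 7.3.2.3 summarises each vital sign "by calculating the mean, standard deviation, median, and range by time point", and adds that "the minimum, maximum, average, and last post-baseline value will be determined relative to the baseline vital sign measurements only".
- SAP Section 4 lists one deviation from the protocol, the definition of the efficacy analysis set. The vital-sign outputs in Protocol 7.3.2.3 therefore remain due.

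**The concern.** For saturation a fall is the direction of concern. The protocol's amendment summary, used here only for the purpose of the measurement, says saturation was added to monitor pulmonary toxicity. The highest of several saturation readings is the most reassuring one, so the principle (worst) and the example (highest) select opposite values. Two programmers could each claim to follow SAP 3.1.5 and report different numbers.

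The same sentence handles laboratory results without fixing a direction, by distance from the normal range. Vital signs alone get a single fixed direction, and nothing reverses it for saturation.

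If the example is followed, a low saturation with a higher repeat at the same time point disappears from the mean and range for that visit. There is a second, smaller gap. The protocol requires a post-baseline minimum, but SAP 3.1.5 applies to all descriptive summaries and does not say whether the minimum is derived before or after selection among repeats. If after, it can be overstated as well.

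**Working it through.** The plan has no figure of its own here to reproduce. The check has two parts.

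**1. Does any passage settle the direction for saturation?**

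| Passage | Principle | Direction for saturation |
|---|---|---|
| SAP 3.1.5 | worst | highest (by example) |
| SAP 3.1.7.2 | worst | none given |
| SAP 3.3.3.3 | no rule for repeats | none given |
| SAP 3.8 | no vital-signs subsection | none given |
| Protocol 7.3.2.3 | mean, SD, median, range; post-baseline minimum and maximum | none given for repeats |

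The only stated direction is the wrong one for saturation. The provision on unscheduled visits does not repair this, because it concerns readings outside scheduled visits, not a repeat discarded within one.

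**2. How far could the summary move?**

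Cohort sizes are redacted and no readings are given, so every input below is assumed. At one time point there are *n* patients. One has a low reading *L* and a repeat of 97%; the other *n* − 1 read 97%.

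- Highest value kept: mean = 97, minimum = 97.
- Lowest value kept: mean = 97 − (97 − *L*)/*n*, minimum = *L*.
- Overstatement of the mean = (97 − *L*)/*n*. Overstatement of the minimum = 97 − *L*.

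| *L* | Mean, *n* = 10 | Mean, *n* = 20 | Mean, *n* = 30 | Minimum |
|---|---|---|---|---|
| 94% | 3/10 = 0.30 | 3/20 = 0.15 | 3/30 = 0.10 | 3 |
| 91% | 6/10 = 0.60 | 6/20 = 0.30 | 6/30 = 0.20 | 6 |
| 84% | 13/10 = 1.30 | 13/20 = 0.65 | 13/30 = 0.43 | 13 |

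If one other patient reads 93%, the visit minimum is 93 when the highest value is kept and min(93, *L*) when the lowest is kept. The overstatement of the minimum is then 93 − 93 = 0, 93 − 91 = 2 or 93 − 84 = 9 points.

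Ordinary measurement noise gives a smaller but systematic shift. For two independent normal repeats with within-visit standard deviation *s*, the expected maximum exceeds the true level by *s*/√π, and the expected gap between maximum and minimum is 2*s*/√π. For assumed *s* = 1, 2 and 3 points, the first is 0.56, 1.13 and 1.69, and the second is 1.13, 2.26 and 3.39.

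**The case against.** The strongest reply is that the governing words are already right. SAP 3.1.5 selects the worst observation, the vital-signs direction is only an example, and SAP 3.1.7.2 restates the principle with no direction at all. A careful programmer would take the lowest saturation. That reading is available, but it requires setting aside the only instruction the SAP gives for any vital sign. An example that produces the opposite of its rule needs correcting.

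Several other points stand and limit the weight of the finding:

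- The rule acts only when readings are repeated at the same scheduled time point. The supplied text asks for repeats only of abnormal blood pressure (Protocol 6.10). A recheck at an unscheduled visit is not assigned to a visit, so it cannot displace a low scheduled reading.
- SAP 3.1.7.2 treats extreme post-baseline values as a separate summary that also draws on unscheduled visits. This suggests, without stating it, that the minimum uses all readings.
- Readings remain in the listings, and clinically significant abnormalities are reported and tabulated as adverse events. The study ended early and the SAP itself calls the sample small, so reviewing the listings is practical.
- The sub-protocol was not supplied and most of the schedule of events is redacted. The absence of a contrary rule is established only for the text available.
- The illustration restates its assumed inputs. It shows the mechanism and a range, not an expected size.

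These points bear on how often and how much the summary could be wrong. A listing or an adverse event record does not put an omitted reading back into the table.

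**Conclusion.** The concern holds. As written, the SAP's example keeps the best saturation reading where its principle asks for the worst, and no supplied passage resolves the conflict. The wording problem is certain; its practical effect is not. The effect runs from none, where nothing is repeated, to the full gap between the two readings in a visit minimum. For the mean it is that gap divided by the number of patients, under the assumed readings and cohort sizes above. It is confined to descriptive safety summaries at time points with repeats; adverse event counts and efficacy results do not change.

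For blood pressure, heart rate, respiratory rate and temperature, taking the higher repeat is a defensible reading of worst. For these, only the order in which the minimum is derived is open. The correction should be made because it costs almost nothing and removes a bias in the direction that hides a safety signal.

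**What to change.** Three edits to the SAP:

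1. In 3.1.5, change the vital-signs example to: *the highest value for vital signs, except the lowest value for oxygen saturation*.
2. In 3.1.7.2, refer to 3.1.5 for the meaning of worst.
3. Add: *The post-baseline minimum and maximum of each vital sign (Protocol 7.3.2.3) are derived from all post-dose readings, scheduled and unscheduled, before any selection among repeats.*

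The first edit is the essential one. The third closes the related gap for all vital signs and agrees with how SAP 3.1.7.2 already treats unscheduled readings in extreme-value summaries.

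The cost is one clause, one cross-reference, one sentence and one exception in the programming. All readings are already collected and listed, so no new data or tables are needed. If the SAP can no longer be amended, the saturation exception can be applied and reported in the clinical study report as a deviation from the SAP, as Protocol Section 7 provides.

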6.10. Vital Signs

Vital signs should include the following:

- Systolic and diastolic blood pressure (BP) (For more information on normal ranges of BP by height and weight refer to Appendix H)
- Heart rate, respiratory rate, oxygen saturation, body temperature

For patients, < 18 years of age, blood pressure should be taken manually (auscultatory method) using an appropriate-sized cuff for the patient's arm dimension with feet on the floor. Care should be taken to measure blood pressure prior to other assessments and once child has been calm for a sufficient amount of time. Abnormal blood pressures should be repeated. If (automated) oscillometric methods must be used, then abnormal values should be confirmed with a manual measurement.

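### Baseline keeps the latest vital-sign reading but post-dose summaries keep the highest, so wherever same-visit repeats are recorded the mean change is biased upward with no drug effect

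*SAP*

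**What the plan says.** **Before dosing.** SAP 3.1.3: "Baseline value will be defined as the most recent non-missing value obtained prior to administration of first dose of study treatment". Change is the post-baseline value minus this one. SAP 3.1.7.2 adds: "Unscheduled visit prior to first dose of study drug may be included in the calculation of baseline value if applicable".

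**After dosing.** The rule in SAP 3.1.5 begins "If multiple results are available for a post-dose assessment at the same scheduled time point". It selects the worst observation, which for vital signs means that "the highest value for vital signs) will be used in all descriptive summaries". SAP 3.1.7.2 repeats the principle: "If more than one assessment is available for a given post-baseline visit, the worst observation will be selected for visit-based summaries". Neither section extends a worst-value rule to baseline.

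**Where repeats come from.** Protocol 6.10, in the paragraph that opens with patients under 18, makes manual blood pressure the default and asks for abnormal pressures to be repeated. It continues: "If (automated) oscillometric methods must be used, then abnormal values should be confirmed with a manual measurement". No equivalent instruction is given for adults or for the other vital signs.

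**What is reported.** Protocol Table 6 lists change from baseline in targeted vital signs as a Phase 2 safety endpoint. Protocol 7.3.2.3 plans mean, SD, median and range by time point. SAP 3.3.3.3 includes oxygen saturation among the vital signs. SAP 3.3.3.7, by contrast, averages ECG triplicates before analysis.

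**The concern.** The two sides of one subtraction follow different rules. A reading repeated because it was high will, on average, be followed by a lower one. At baseline the plan keeps that lower repeat; after dosing it keeps the higher of the pair. The difference is therefore more than a cautious choice of value: it produces a rise where none exists. The study has a single arm per cohort and no randomised control, so no comparison cancels the artefact.

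The same rule gives the manual confirmation in Protocol 6.10 no precedence. If the automated reading is higher, it is the one summarised.

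For oxygen saturation, and for a blood pressure repeated because it was low, the highest reading is the most reassuring one. There the rule hides deterioration.

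**Working it through.** The documents give no figure on this point, so there is none to reproduce. The selection rules come from SAP 3.1.3, 3.1.5 and 3.1.7.2. Every SD, mean and threshold below is an assumption.

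**1. Direction.** The maximum of a set of readings is never below its last member. For two exchangeable normal readings with within-patient SD s, the expected maximum minus the expected last is s/√π = 0.564s. If a share f of patients has one repeat, whatever the first value was, the mean shift is f × 0.564s. With s = 5 this is 0.10 × 2.82 = 0.28 mmHg at f = 10%, and 0.25 × 2.82 = 0.71 at f = 25%.

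**2. Repeats triggered by a high reading.** Simulation of 2,000,000 patients, no true change, one repeat when the first systolic reading is at or above the threshold; baseline = last, post-dose = maximum:

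| Mean, between-patient SD, threshold | Within-patient SD | Repeated | Spurious mean change | At/above threshold, baseline → post |
|---|---|---|---|---|
| 115, 9, 130 | 5 | 7.2% | +0.40 | 3.6% → 7.2% |
| 115, 9, 130 | 8 | 10.6% | +1.08 | 3.9% → 10.6% |
| 125, 12, 140 | 5 | 12.4% | +0.58 | 8.0% → 12.4% |
| 125, 12, 140 | 8 | 14.9% | +1.27 | 7.7% → 14.9% |
| 125, 12, 140 | 10 | 16.8% | +1.90 | 7.8% → 16.8% |

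In these settings the first reading exceeds its repeat in 68-82% of repeated cases. The repeat falls below the threshold in 36-63% of them. If automated readings run 3-5 mmHg high (mean 115, between-patient SD 9, within-patient SD 6, threshold 130), the automated value is kept in 85-89% of cases and the spurious change is 1.20-1.83 mmHg.

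**3. Which side contributes.** Let s be the within-patient SD, b the between-patient SD, σ = √(s² + b²), and c the distance from mean to threshold divided by σ. Replacing a high first reading by its repeat lowers the mean by (s²/σ)φ(c). With s = 8, b = 12 and a threshold 15 above the mean: σ = 14.42, c = 1.04, φ(c) = 0.232, so the baseline mean is lowered by (64/14.42) × 0.232 = 1.03. The rest of the 1.27, about 0.24, comes from the post-dose maximum. The mismatch creates the bias, and most of it enters through the baseline rule.

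**4. Matched rules under no effect.** Last/last, max/max and mean/mean all give 0.0 (within ±0.01) in every setting. This requires the same repeat practice before and after dosing.

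**5. Matched rules with a true rise of 5 mmHg** (s = 8, b = 12). After dosing the threshold is only 10 above the mean: 10/14.42 = 0.693, φ = 0.314, so last lowers the post-dose mean by 4.44 × 0.314 = 1.39. Last/last then reports 5 − (1.39 − 1.03) = 4.64. Averaging halves each term: 5 − 0.18 = 4.82. With no between-patient spread and a threshold 8 above the mean, the corresponding values are 3.96 and 4.48.

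**6. Dilution.** If adolescents were 10-20% of patients (assumed) and adults had no repeats, the overall shift would run from 0.1 × 0.4 = 0.04 to 0.2 × 1.9 = 0.38 mmHg.

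**The case against.** The best case against the point is that it is narrow and partly covered.

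- **Scope.** The instruction to repeat sits in the under-18 paragraph of Protocol 6.10 and covers blood pressure only. Automated measurement is the exception there, and it prevails only when it is the higher reading. This stands and limits the point.
- **Unscheduled readings.** SAP 3.1.7.2 does not assign these to a visit, so post-dose repeats entered that way leave the by-visit means. This stands for the post-dose maximum. It does not clear the baseline side, because the same section allows unscheduled pre-dose readings into baseline.
- **Other outputs.** Protocol 7.3.2.3 also plans minimum, maximum, average and last post-baseline values relative to baseline. SAP 3.1.5 lists all results with abnormal values flagged, and SAP 3.3.3 has clinically significant abnormalities reported as adverse events. A reader might infer that confirmatory readings vanish from the report; they do not. But the by-visit mean still carries the bias. SAP 3.8 has no vital-signs section, so that mean rests on Protocol 7.3.2.3 and the general SAP rules.
- **Consequence.** These are descriptive safety data in an uncontrolled study that was terminated early. Sampling noise may exceed 1-2 mmHg. This stands, and it keeps the point minor.
- **Remedy.** Using the last reading on both sides also gives zero under no effect, but it attenuates a real rise more than averaging does.

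**Conclusion.** The mismatch is in the current text, and its direction does not depend on any assumption. It is a minor point. Among patients subject to the repeat rule, the spurious rise is about 0.4-1.9 mmHg, given within-patient SD 5-10, between-patient SD 9-12 and 7-17% of readings repeated for being high at the same scheduled time point. It is smaller overall if only adolescents are repeated.

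Three stronger readings are not supported:

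- A rise of 1.0-3.3 mmHg. This appears only if all patients share one true pressure, so that every high reading is noise. At the same repeat rates, a between-patient SD of 12 brings 1.0, 2.0 and 3.3 down to 0.6, 1.4 and 2.5.
- A rise across the whole trial, or in heart rate. The documents state no trigger for adult or heart-rate repeats, so any effect there depends on site practice.
- The post-dose maximum as the sole culprit. Most of the shift comes from the latest-value rule at baseline.

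**What to change.** In SAP 3.1.3, 3.1.5 and 3.1.7.2, use one rule before and after dosing for by-visit means and change from baseline: the mean of same-visit readings, as SAP 3.3.3.7 does for ECG triplicates. State that a manual confirmation replaces the automated reading it checks. Reserve worst values for labelled shift and extreme-value tables, and define the direction of worst for each parameter, including oxygen saturation and low blood pressure.

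The cost is SAP wording and one derivation flag. By-visit means will look less extreme. Because only high readings are repeated, a true rise is slightly attenuated: about 4.8 reported for a true 5 mmHg in the assumed model (within-patient SD 8, between-patient SD 12), and about 4.6 where a manual reading replaces an automated one. Worst values remain in the extreme-value tables and all readings remain in the listings, so no safety information is lost.
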